- **7.5.6** XR-NTX and Renal Impairment. A pharmacokinetic analysis indicated that mild renal insufficiency (creatinine clearance of 50-80 mL/min) had little or no influence on XR-NTX pharmacokinetics and that no dosage adjustment is necessary. Pharmacokinetics of XR-NTX have not been evaluated in subjects with severe renal insufficiency, thus individuals with severe renal abnormalities will not be included in this study.
- **7.5.7 XR-NTX and Gender.** In a study of healthy subjects (n=18 females; 18 males), gender did not influence the pharmacokinetics of XR-NTX.
- **7.5.8 XR-NTX and Drug-Drug Interactions.** Studies evaluating drug-drug interactions have not been performed.
- **7.5.9** XR-NTX and Reversal of Blockade for Pain Management. In an emergency situation, suggestions for pain management are regional anesthesia or non-opioid analgesics. If opioids are required, they must be provided in a setting where establishment and maintenance of a patent airway and assisted ventilation are readily available from persons trained in the use of anesthetic drugs and management of respiratory depression.

- **7.5.10** Depression and Suicidality. In controlled trials among patients with alcohol dependence, AEs of a suicidal nature (ideation, attempts and completed suicides) were infrequent, but more common in patients treated with XR-NTX than placebo (1%). In some cases, suicidal thoughts or behaviors occurred after study discontinuation but in the context of an episode of depression that began while the patient was on the medication. Two completed suicides occurred in alcohol treatment studies, both in patients treated with XR-NTX, and depression-related events were more common in patients treated with XR-NTX than in those on placebo (1%). However, two studies that have specifically examined the relationship between depression and XR-NTX treatment found that depression and anxiety decrease in association with detoxification and naltrexone treatment (Mysels et al, 2011; Krupitsky et al, 2016)
- **7.5.11** Naltrexone Contraindications. Patients should not receive XR-NTX if they are taking opioid analgesics; have current opioid dependence; are in opioid withdrawal; failed a naloxone challenge or have a positive urine screen for opioids; exhibited hypersensitivity to naltrexone, PLG, carboxymethylcellulose, or any other components of the diluent; or have acute hepatitis or liver failure.

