Subjects are admitted to the inpatient unit, randomized to one of the two study medication conditions, and will need to demonstrate withdrawal before starting study medications by having a COWS >/= 6 and a SOWS >/= 4. LFX and PGB dosing will begin at 12:00 on day 1 and a study drug taper will be done from days 5-7. Dose times follow the schedule outlined above and adjustments will be made based on BP changes and/or other AEs. Administration of LFX will be withheld or reduced in cases of dizziness or lightheadedness, clinically significant hypotension and/or the BP changes described above. We will explain to participants the importance for adequate oral hydration during the consenting process and throughout the detox. Similar procedures will be applied to PGB in cases of excessive sedation, dizziness, peripheral edema, or other problematic side effects that appear related that medication.

Dosing schedules are in Tables 2 and 3. Assessments for Day 1 through 7 include:

- 1) ECG is obtained before the 12:00 dose of study medications on Day 1 and before the 08:00 dose of study medications on Day 2-7
- 2) VAS is given before the first dose of study medication at 12:00 on Day 1 and before the 16:00 dose on Day 1. On Day 2-7, the VAS is given before the first dose of study medications at 08:00 and before the 16:00 dose of study medications
- 3) ISI given before the 12:00 dose of study medications on Day 1, and before the 08:00 dose of study medications on Days 2-7
- 4) COWS is given around 12:00 on Day 1 before the first dose of study medication; and around16:00 before the next dose of study medication. If subject is admitted without the requisite withdrawal (COWS >/= 6 and SOWS >/= 4), subsequent COWS and SOWS can be administered before the first dose of study medication until dosing criteria is met.
- 5) SOWS-G is given around 12:00 on Day 1 before the first dose of study medication; and around 16:00 before the next dose of study medication
- 6) POSS is given prior to all doses (08:00, 12:00, 16:00 and 20:00) of study medication
- 7) Sitting and standing blood pressure and pulse are taken prior to each dose of study medication and 1 to 2 hours after dosing, (can use manual blood pressure check if considered necessary)
- 8) Weight taken 1x at screen and Day 15 and recorded on the physical form
- 9) Adverse events/SAEs recorded daily
- 10) Concomitant medication records reviewed and recorded each day
- 11) C-SSRS is given at the end of each study day

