9.1.3 Phase 3: Inpatient XR-NTX Dosing (Day 8 or 9)

On day 8, subjects will be offered an injection of XR-NTX following naloxone challenge starting with a split dose an option of 0.2 mg first, wait 10-20 minutes, then 0.6 mg (0.8 mg I.M of naloxone total) An injection of Vivitrol is optional, only if the subject is interested in the XR-NTX treatment), and only if the COWS does not rise above 10 (COWS) within 15-30 minutes after the challenge. Subjects will be offered a second XR-NTX dose in the outpatient research clinic 4 to 5 weeks after the Day 8/9 injection if they wish to continue XR-NTX and have been unable to find a community provider. Subjects who fail the naloxone challenge on Day 8 will receive symptomatic treatment, observed until symptoms resolve, and be offered an opportunity for a repeat

challenge and injection on day 9. Note:

Note: XRNT may be given to patients after a Naloxone challenge in Pts about to go AMA from hospital if the naloxone challenge results suggest an absence of physiologic dependence.

The following assessments will be conducted before the XR-NTX injection:

- 1) CK test drawn before IM Injection of naloxone (PGB can elevate CK)
- 2) Vital Signs (blood pressure sitting)
- 3) Adverse Events Review
- 4) Urine Pregnancy Test
- 5) VAS scale
- 6) ISI
- 7) SOWS-G
- 8) POSS
- 9) UDS
- 10) Urine Fentanyl test
- 11) urine xylazine test
- 12) COWS
- 13) Naloxone Challenge*
- 14) Concomitant Medication Review
- 15) C-SSRS

ADMINISTRATION OF EXTENDED-RELEASE NALTREXONE

The following assessments will be conducted after the XR-NTX injection:

- 1) CGI
- 2) HAM-A, HAM-D
- 3) Inspection of injection site
- 4) Comfort medication(s) (PRN)

(It is permissible to give comfort medication at visit 8 for Day 8, 9, and at Day 10 for visit 10, 11, 12, 13, 14 and 15. No comfort medication will be given by the study after Day 15. Comfort medication needed after Day 15 will be considered non-study follow-up care. Patients can get comfort medications even if they don't opt for XR-NTX).

* Optional. Subject can opt not to receive this treatment. The Study Physician will discuss with the subject other available options. All assessments for Day 8 except the challenge and XR-NTX will still be collected.

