10.8 EARLY WITHDRAWAL OF SUBJECTS

All randomized subjects are included in the intent-to-treat analysis. After day 15, or at termination for patients who discontinue the trial prematurely, subjects will be asked to complete the following procedures and assessments: physical exam, vital signs, weight, adverse events; concomitant medications; blood samples for chemistry, CK, CBC with diff and PLT, liver function; urinalysis with reflex microscopy, urine drug toxicology screen; a fentanyl urine test, a xylazine urine test, a pregnancy test for females; and the Clinical Global Impression. ECG will be obtained for early terminators. Subjects will be referred to the most appropriate and available treatment and attempts will be made to obtain these data unless the subject requested they not be contacted or cannot be located.

Subjects will be informed at the consent session that medications could be discontinued if (at the discretion of the principal investigator or site physician): 1) Intolerable side effects occur, or 2) Extreme lab values with a repeat test occur, or that he/she may be discontinued from the study due to

development of psychiatric or medical problems that require a more intensive intervention than provided by the study. Examples are psychiatric symptoms that require inpatient treatment (suicidal ideation, acute psychosis, acute mania); clinical deterioration or a change in status that requires admission to an inpatient medical service; or development of behaviors that compromise safety of the subject or staff. Referrals for care will be made and reasons for subject discontinuation from the study medication and/or clinical trial will be documented on the End of Study Final Evaluation Form.

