10.11 STUDY MEASURES; SEE TABLES 1 FOR SCHEDULES OF ADMINISTRATION

- 1. **Medical History:** Done by the appropriate clinical delegated individual at screening
- 2. Physical/Weight: Done at Screen; and at Day 15
- 3. Pulse and blood pressure: done sitting and standing 1X at screen, done Day 1 through Day 7 done before receiving Study Medication and 1 2 hours after receiving medication, 1X on Day 8, 1X (sitting only) on Day 10 (sitting only), and 1X on Day 15
- 4. ECG: 1X at Screen, 1X each day for Day 1 through Day 7
- 5. Complete Blood Count with diff and PLT: Done at Screening and Day 10
- **6.** Chemistry and calcium: Done at Screening and at Day 10 or Day 15 if not obtained at Day 10
- 7. Magnesium Screening (magnesium need not be repeated at EOS)
- 8. Creatine Kinase at screening and Day 8, and early termination
- 9. Hepatitis B and C done at screening
- 10. Urinalysis with reflex microscopy: Done at Screening and Day 10
- **11. Urine Toxicology Drug Screen.** CLIA Waived and FDA approved on-site test with Buprenorphine, or get an additional buprenorphine test, done at screen, day 8/9, day 10, and day 15.
- **12. Urine Fentanyl**. Done at Screen, Day 1, Day 8/9, Day 10, and Day 15.
- 13. Urine Xylazine . Done at Screen, Day 1, Day 8/9, Day 10, and Day 15.
- 14. Urine pregnancy test: Screen and Day 1, Day 8/9 prior to the XR-NTX injection, and at Day 15
- 15. Adverse Events: Collected by research staff at each visit, Day 1 through Day 15
- **16. Clinical Global Impression Scale (CGI;** Guy,1976): A brief severity rating of overall health at time of interview using a 7-point Likert scale. Completed by a study staff person and the subject. Administered at day 1, day 8, and EOS
- 17. Clinical Opioid Withdrawal Scale (COWS; Wesson & Ling, 2003): An 11-item, staff administered instrument that measures objective signs of opiate withdrawal. Done 1X at screen, 2X daily Day 1 through Day 7, 2X (naloxone challenge) on Day 8* (optional), and 1X on Day 10, and 1X Day 15
- **18. Short Opioid Withdrawal Scale** (SOWS-Gossop; Gossop, 1990): A 10-item, staff administered scale that measures patient's perceptions of opiate withdrawal. Done 1X at screen; 2X daily Days 1 Day 7; and 1X on Days 8,10, and 15.
- **19. CONCOMITANT Medication** (CONMEDS): Any prescribed or non-illicit non-Study Medications used 30 days before screening, and on Day 1 through EOS

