19.2 MEDICATION DISCONTINUATION CRITERIA

All randomized subjects are included in the intent-to-treat analysis. All subjects who prematurely discontinue treatment will be scheduled for a final evaluation and end-of trial visit (unless these two fall within 2 weeks of each other), and the follow up visit. Subjects are not dropped from all study activity unless they request to not be contacted or cannot be located for assessment.

Subjects will be informed at the consent session that medications may be held or discontinued due to intolerable side effects, hypotension or other problematic cardiovascular effects, or extreme lab values confirmed by a repeat test. (AST or ALT levels greater than 4 times upper limit of normal; elevated BUN, creatine kinase, or other evidence of renal damage). Subjects will also be informed at the consent session that he or she may be discontinued from study treatment due to: 1) Development or exacerbation of significant psychiatric or medical symptoms which necessitate admission to a medical unit or an intervention different from that provided by the protocol; 2) Clinical deterioration for any reason or a clinical status which necessitates inpatient admission; 3) Prolonged QTc after repeat ECG; 4) Blood pressure is less than 90 mm Hg (systolic) or less than 60 mm Hg (diastolic). For sitting to standing blood pressure (orthostatic change), if there is a change in systolic blood pressure of more than 20mm or diastolic blood pressure more than 10mm HG, the dosing nurse or physician may hold the lofexidine or pregabalin dose until the next dose and then recheck (can use manual blood pressure check if considered necessary). If at any point blood pressure is less than 90/60 the nurse or physician should also hold the lofexidine or pregabalin dose and consult a study physician. If for any dose, the blood pressure results remain below the previously stated minimum mmHg by the next scheduled dose, the next dose may be reduced or withheld. Dosing discontinuations can be discussed with the Lead PI and the medical monitor if it impacts subject continuation in the dosing part of the study. The reason the subjects misses their next dose of Study Medication or discontinues from Study Medication must be documented in the subject's casebook

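### No AST/ALT, BUN or CK sample is scheduled on the seven dosing days, and chemistry is first repeated on Day 10, after XR-NTX in those injected

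*Combined protocol and SAP*

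**What the plan says.** **Criteria.** Under section 19.2, subjects are told at consent that "medications may be held or discontinued due to intolerable side effects" and for several other reasons, among them "extreme lab values confirmed by a repeat test. (AST or ALT levels greater than 4 times upper limit of normal; elevated BUN, creatine kinase", with further signs of renal damage also named. Section 10.8 gives a shorter version, at the discretion of the investigator or site physician: "Extreme lab values with a repeat test occur".

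**Dosing.** Section 9.1.2: "LFX and PGB dosing will begin at 12:00 on day 1 and a study drug taper will be done from days 5-7". Tables 2 and 3 put the last dose at 20:00 on Day 7.

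**Sampling.** Section 10.11, item 6: "Chemistry and calcium: Done at Screening and at Day 10 or Day 15 if not obtained at Day 10". Item 8: "Creatine Kinase at screening and Day 8, and early termination". Table 1 agrees with both and adds chemistry at the early-termination visit. The Day 1-7 assessment list in 9.1.2 has ECG, blood pressure, pulse and rating scales, but no blood draw.

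**Day 8.** Section 9.1.3 places the CK draw ahead of naloxone: "CK test drawn before IM Injection of naloxone (PGB can elevate CK"). XR-NTX follows on Day 8 or 9 for those who want it and pass the challenge. Section 7.5.11 lists among the reasons not to give it "or have acute hepatitis or liver failure".

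**Use of the data.** Section 13.4.3 compares the arms on Day 8 CK above three times the screening level. Section 13 has no comparison of AST, ALT or BUN; section 10.12 says only that laboratory results will be considered in assessing safety.

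**The concern.** A laboratory criterion that needs an abnormal value and a confirming repeat needs at least one result while drug is being given. The schedule supplies none. The other measured criteria in 19.2 do have scheduled inputs: a daily ECG for QTc, and blood pressure before and after each dose. The gap therefore looks like a mismatch between the criteria and the schedule. It matters somewhat more here because section 3.0 says that the two drugs have not been used together, and section 13.2 makes safety part of the primary goal.

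The second issue is what the chemistry data can show. In a completer, the only scheduled on-study chemistry comes after study drug has ended and, in those injected, after XR-NTX. Receipt of XR-NTX is a post-randomization outcome that the second objective in 8.2 hopes pregabalin will increase. Subjects who leave early are sampled at exit instead. A difference between arms in AST, ALT or BUN would therefore mix pregabalin, naltrexone and who came back.

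**Working it through.** The plan states no figure on this point, so the check is a count of scheduled samples and some elapsed-time arithmetic.

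**Samples during dosing**

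- Dose times (Tables 2 and 3): 3 on Day 1, then 4 on each of 6 days; 3 + 4 × 6 = 27.
- Chemistry (Table 1, 10.11): screening, Day 10, Day 15 only if Day 10 was missed, early termination. On Days 1-7: 0.
- CK (Table 1, 10.11): screening, Day 8, early termination. On Days 1-7: 0.

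**Time from last dose to sample**, assuming an 08:00 draw (the documents give no clock time)

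| Sample | Hours after 20:00 on Day 7 | Pregabalin half-lives (6.3 h, section 7.2.5) | Lofexidine half-lives (about 12 h, section 7.4) |
|---|---|---|---|
| Day 8 CK | 4 + 8 = 12 | 12/6.3 = 1.9 | 12/12 = 1.0 |
| Day 10 chemistry | 4 + 24 + 24 + 8 = 60 | 60/6.3 = 9.5 | 60/12 = 5.0 |

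At 60 hours the fraction of drug left is 0.5^9.5, about 0.1%, for pregabalin and 0.5^5, about 3%, for lofexidine. Table 1 allows Day 10 to slip by up to 2 business days: 117 hours at 17:00 on Day 12, or 165 hours at 17:00 on Day 14 if a weekend intervenes. These figures describe drug exposure only. The documents do not say how long a change in AST, ALT or BUN would stay detectable.

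**Age of the chemistry when XR-NTX is given on Day 8 or 9** (screening from Day -30 to Day -1, Figure 1)

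- Shortest: screened Day -1, injected Day 8. With no Day 0, 1 + 7 = 8 days.
- Longest: screened Day -30, injected Day 9. With no Day 0, 30 + 8 = 38 days; 39 if a Day 0 is counted.
- Range: about 8 to 39 days.

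**Order of events by type of subject**

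| Subject | Chemistry after screening | Relation to XR-NTX |
|---|---|---|
| Completer, injected | Day 10 (Day 15 if missed), if the subject returns | 1-2 days after injection if Day 10 is on time |
| Completer, not injected | Same | None received |
| Leaves early | At exit | May receive XR-NTX on leaving (7.5.2, Table 1); order of draw and injection not stated |

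The documents give no expected XR-NTX uptake, so the exposed share at Day 10 could be anything from 0 to 100% in either arm. The size of any resulting bias cannot be computed.

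**The case against.** The strongest reply is that 10.8 and 19.2 do not promise scheduled monitoring. The wording is permissive, and 10.12 allows additional tests whenever the investigator finds them necessary and asks that significantly abnormal values be repeated. Subjects are inpatients whose adverse events are reviewed daily. This stands. A reader might infer that the laboratory criteria cannot operate at all; the documents do not support that. They can operate, but during dosing only if someone decides to order a test.

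A reader might also infer that the laboratory safety data as a whole are contaminated. That is too broad. The one laboratory value with a planned comparison, Day 8 CK, is drawn before naloxone and XR-NTX. The problem is confined to AST, ALT, BUN and the rest of the chemistry panel, which section 13 does not formally compare. It still matters, because 10.12 uses laboratory results to judge safety.

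It can be said that 10.8 and 19.2 speak of medications generally and so could cover XR-NTX, for which the Day 8 CK and the Day 10 chemistry (ahead of a second injection) are available. That reading is possible, but it leaves the criteria without a scheduled input for pregabalin and lofexidine.

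Liver risk is screened at entry by ALT/AST, Child-Pugh score and hepatitis tests. That lowers the likely number of events but does not supply an on-drug value. The wording of the consent form cannot be judged, because it is not part of the material available.

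**Conclusion.** The point holds in a limited form. No AST/ALT, BUN or CK sample is scheduled on any of the 7 dosing days, so during dosing the laboratory criteria in 10.8 and 19.2 rest on unscheduled, discretionary tests. AST, ALT and BUN are next scheduled on Day 10, when pregabalin effects can no longer be separated from XR-NTX receipt or from attendance. An intention-to-treat contrast at Day 10 would still describe the whole treatment sequence if everyone attended, but not pregabalin's own effect on chemistry.

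The count of zero follows directly from the documents. The 60 hours rests on an assumed 08:00 draw, and the 8 to 39 days depends on the screening date and on how days are numbered. The amount of confounding is unknown. This should be corrected, but it does not touch the primary analysis or the CK comparison.

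**What to change.** 1. **Reconcile the text.** Sections 10.8 and 19.2 must be brought into line with Table 1 and 10.11. The clinical leads decide whether the laboratory criteria stand and which sample feeds them; otherwise the text should say that they apply only to unscheduled tests. Section 10.8 also lists bloods, including chemistry and CK, after Day 15. Table 1 makes Day 15 chemistry conditional on a missed Day 10 and has no CK then, and the Day 15 list in 9.1.5 has no blood draw. These need the same reconciliation. No clinical rule is proposed here.

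2. **Add chemistry to the Day 8 draw, for the safety data.** Run the panel on the blood already taken for CK, before naloxone and XR-NTX. Use that value for the between-arm chemistry summary, and show exit samples from early leavers separately. Leave the Day 10 chemistry (Day 15 if missed) in place as the later look.

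**Cost.** An amendment to Table 1, 9.1.3 and 10.11, and one extra chemistry panel per subject reaching Day 8, with no extra venipuncture. That is at most 90 panels. If the 40% dropout assumed in 13.2 all fell before Day 8, it would be 90 × 0.60 = 54.

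**Limits.** The Day 8 sample removes the dependence on XR-NTX and on outpatient attendance, but not on staying to Day 8. It also comes after the last dose, so the dosing days with a scheduled sample remain 0 of 7. That gap belongs to step 1.

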20.0 SUBJECT STIPEND AND REIMBURSEMENTS

Each site will reimburse subjects as per the procedures below:

TABLE 6: PENN SUBJECT STIPENDS AND REIMBURSEMENTS

Screen	Day1	Day2	Day3	Day4	Day5	Day6	Day7	Day8	Day9	Day10	Day15
	InPatient Admission	InPt	InPt	InPt	InPt	InPt	InPt	InPt VIVITROL	InPt optional	F/up	F/up
50.00	125	125	125	125	125	125	125	125	125	50	50
10.00	10.00							10.00*	10.00*	10.00	10.00
Total											
60.00	135.00	125	125	125	125	125	125	135.00	135.00	60.00	60.00

This study will use Greenphire ClinCard as the payment method. The patient's social security number will be collected but not used or stored in any data records kept by the research study

staff. Subjects will receive \$50 for completing screening assessments and a maximum of \$10.00 total for travel reimbursement for screening. During this inpatient phase of the study, patients will be reimbursed \$125.00 per day for completing assessment for a possible total of up to \$1000.00, plus \$20.00 for travel on days 1 and 8 (admission and discharge) for a total of \$1200. If subjects are inpatient for 9 days, however, as seen in Table 8 above, the maximum reimbursement for completing all assessments for screening and the 9 inpatient days will be \$1175, plus a total of \$20.00 for travel reimbursement for Screening on Days 1 and 9 for a maximum total for completing all assessments of \$1205.00. For the follow-up visits-Day 10 and Day 15, subjects will receive \$50.00 for completing all outpatient assessment for a total of up to \$100.00, plus a total of \$20.00 for travel reimbursement for a total of \$120.00. The maximum that a subject can receive for screening, a 9-day inpatient stay completing all assessments, plus outpatient visits and travel reimbursement is \$1325.00 for the study. The maximum that a subject can receive for the 8-day inpatient stay, completing all assessments plus travel reimbursement is \$1200.00.

TABLE 7: MOUNTAIN MANOR SITE SUBJECT STIPENDS AND REIMBURSEMENTS

	Screen	Day1 InPt Admt	Day 2 InPt	Day 3 InPt	Day 4 InPt	Day 5 InPt	Day6 InPt	Day7 InPt	VIVITROL	Day 9 Possible) InPt VIVITROL	Day 10 F/up	Day 15 F/up
Assessments Total	50	125	125	125	125	125	125	125	125	125	50	50
Travel	10	10							10*	10*	10*	10*
Total	60	135	125	125	125	125	125	125	135	135	60	60

This study will use Clinical Trials Payer (CT Payer) gift cards as the method of payment.

- Subjects will receive \$50 for completing assessments during the screening visit.
- During the inpatient phase of the study, upon completion of all assessments on each inpatient day, patients will be compensated \$125.00 (Days 1-8; possibly including day 9).
- For the follow-up visits-Day 10 and Day 15, subjects will receive \$50.00 for completing all assessments. In addition, subjects will receive \$10.00 reimbursement for travel for the screening visit, for travel on the day of inpatient admission and discharge*, and travel for the day 10 and day 15 follow-up visits. The maximum that a subject can receive for a 9-day inpatient stay plus outpatient visits, and travel reimbursement is \$1325.00. The maximum that a subject can receive for the average 8-day inpatient stay and completing assessments plus travel reimbursement is \$1200.00. You will only receive reimbursement for travel if you are traveling to or from the treatment center for study related reasons. You will receive your CT Payer Card and be reimbursed during screening but will not be reimbursed for other study procedures until you are released from inpatient care.

Please note: In order to be compensated for participation in this study, you must provide your Social Security Number. Additionally, please note that the University of Pennsylvania is required to report to the IRS any cumulative payments for participation in research studies that exceed a total of \$600 in a calendar year.

TABLE 8: COLUMBIA SITE SUBJECT STIPENDS AND REIMBURSEMENTS

Screen	Day1	Day2	Day3	Day4	Day5	Day6	Day7	Day8	Day 9	Day10	Day 15
	InPt Admt	InPt	optional	OutPt	OutPt						

56

								VIVITROL		F/up	F/up
50.00	50.00	50.00	50.00	50.00	50.00	50.00	50.00	50.00	50.00	50.00	50.00
10.00	10.00							10.00	10.00*	10.00	10.00
Total											
60.00	60.00	50.00	50.00	50.00	50.00	50.00	50.00	60.00	60.00	60.00	60.00

You will be paid during the study. The study involves time-consuming assessments that are not included in usual treatment and you will be paid for the time and travel needed to complete assessments. You will receive \$50 for completing assessments during the screening visit. During the inpatient phase of the study, upon completion of all assessments on each inpatient day, you will be compensated \$50 for a possible total of up to \$450 if you are inpatient for 9 days, however as seen above, the expected average inpatient stay is 8 days. For the follow-up visits-Day 10 and Day 15, you will receive \$50 for completing each outpatient assessment for a total of up to \$100. In addition, you will receive \$10 reimbursement for travel for the screening visit, travel on inpatient admission day and discharge from inpatient, and \$50 for the day 10 and day 15 follow-up visits. The maximum that you can receive for a 9 day inpatient stay plus outpatient visits, and travel reimbursement is \$650.00 for the study. The maximum that you can receive for the average 8-day inpatient stay and completing assessments plus travel reimbursement is \$600.00.

Please note: In order to be compensated for your participation in this study, you must provide your Social Security Number. For compensation of \$600 or more, we are required by law to reports your earning to the IRB. Therefore, your Social Security Number and amount earned will be reported, and you will receive the appropriate IRS form at the end of the year in which you were paid. Please not that payments for this study may affect your eligibility for Medicaid and other city and state support services. No information about which study you participated in will be provided to the IRS.

